## 10.6. Appendix 6: Kidney Safety Monitoring Guidelines

### 10.6.1. Laboratory Assessment of Change in Kidney Function and Detection of Kidney Injury

Standard kidney safety monitoring requires assessment of baseline and postbaseline serum creatinine (Scr measurement to eGFR [Scr-based eGFR] or [eCrCl]). Baseline and postbaseline Scys makes it feasible to distinguish AKI from other causes of Scr increase. If Scr increase is confirmed after baseline, then reflex measurement of Scys is indicated to estimate the combined Scr-Scys eGFR calculation (for adults only).

Regardless of whether kidney function monitoring tests are required as a routine safety monitoring procedure in the study, if the investigator or sponsor deems it necessary to further assess kidney safety and quantify kidney function, then these test results should be managed and followed per standard of care.

### 10.6.2. Age-Specific Kidney Function Calculation Recommendations

#### 10.6.2.1. Adults (18 Years and Above)—2021 CKD-EPI Equations

2021 CKD-EPI Scr Only	Scr (mg/dL)	Scys (mg/L)	Recommended eGFR Equation 
Female	if $\leq 0.7$	N/A	$eGFR = 143 \times (Scr/0.7)^{-0.241} \times (0.9938)^{Age}$
Female	if $> 0.7$	N/A	$eGFR = 143 \times (Scr/0.7)^{-1.200} \times (0.9938)^{Age}$
Male	if $\leq 0.9$	N/A	$eGFR = 142 \times (Scr/0.9)^{-0.302} \times (0.9938)^{Age}$
Male	if $> 0.9$	N/A	$eGFR = 142 \times (Scr/0.9)^{-1.200} \times (0.9938)^{Age}$
2021 CKD-EPI Scr-Scys Combined	Scr (mg/dL)	Scys (mg/L)	Recommended eGFR Equation 
Female	if $\leq 0.7$	if $\leq 0.8$	$eGFR = 130 \times (Scr/0.7)^{-0.219} \times (Scys/0.8)^{-0.323} \times (0.9961)^{Age}$
Female	if $\leq 0.7$	if $> 0.8$	$eGFR = 130 \times (Scr/0.7)^{-0.219} \times (Scys/0.8)^{-0.778} \times (0.9961)^{Age}$
Female	if $> 0.7$	if $\leq 0.8$	$eGFR = 130 \times (Scr/0.7)^{-0.544} \times (Scys/0.8)^{-0.323} \times (0.9961)^{Age}$
Female	if $> 0.7$	if $> 0.8$	$eGFR = 130 \times (Scr/0.7)^{-0.544} \times (Scys/0.8)^{-0.778} \times (0.9961)^{Age}$
Male	if $\leq 0.9$	if $\leq 0.8$	$eGFR = 135 \times (Scr/0.9)^{-0.144} \times (Scys/0.8)^{-0.323} \times (0.9961)^{Age}$
Male	if $\leq 0.9$	if $> 0.8$	$eGFR = 135 \times (Scr/0.9)^{-0.144} \times (Scys/0.8)^{-0.778} \times (0.9961)^{Age}$
Male	if $> 0.9$	if $\leq 0.8$	$eGFR = 135 \times (Scr/0.9)^{-0.544} \times (Scys/0.8)^{-0.323} \times (0.9961)^{Age}$
Male	if $> 0.9$	if $> 0.8$	$eGFR = 135 \times (Scr/0.9)^{-0.544} \times (Scys/0.8)^{-0.778} \times (0.9961)^{Age}$

### 10.6.3. Adverse Event Grading for Kidney Safety Laboratory Abnormalities

AE grading for decline in kidney function (ie, eGFR or eCrCl) will be according to KDIGO criteria.

## 10.7. Appendix 7: ECG Findings of Potential Clinical Concern

ECG Findings That May Qualify as AEs

 
Marked sinus bradycardia (rate <40 bpm) lasting minutes.
 
New PR interval prolongation >280 ms.
 
New prolongation of QTcF to >480 ms (absolute) or by <math>\geq</math>60 ms from baseline.
 
New-onset atrial flutter or fibrillation, with controlled ventricular response rate: ie, rate <120 bpm.
 
New-onset type I second-degree (Wenckebach) AV block of >30 seconds' duration.
 
Frequent PVCs, triplets, or short intervals (<30 seconds) of consecutive ventricular complexes.
 

ECG Findings That May Qualify as SAEs

 
QTcF prolongation >500 ms.
 
New ST-T changes suggestive of myocardial ischemia.
 
New-onset LBBB (QRS complex >120 ms).
 
New-onset right bundle branch block (QRS complex >120 ms).
 
Symptomatic bradycardia.
 
Asystole: 
 
In awake, symptom-free participants in sinus rhythm, with documented periods of asystole <math>\geq</math>3.0 seconds or any escape rate <40 bpm, or with an escape rhythm that is below the AV node;
 
In awake, symptom-free participants with atrial fibrillation and bradycardia with 1 or more pauses of at least 5 seconds or longer;
 
Atrial flutter or fibrillation, with rapid ventricular response rate: rapid = rate >120 bpm.
 
 
 
Sustained supraventricular tachycardia (rate >120 bpm) ("sustained" = short duration with relevant symptoms or lasting >1 minute).
 
Ventricular rhythms >30 seconds' duration, including idioventricular rhythm (HR <40 bpm), accelerated idioventricular rhythm (HR 40 bpm to <100 bpm), and monomorphic/polymorphic ventricular tachycardia (HR >100 bpm [such as torsades de pointes]).
 

- Type II second-degree (Mobitz II) AV block.
- Complete (third-degree) heart block.

#### **ECG Findings That Qualify as SAEs**

- Change in pattern suggestive of new myocardial infarction.
- Sustained ventricular tachyarrhythmias (>30 seconds' duration).
- Second- or third-degree AV block requiring pacemaker placement.
- Asystolic pauses requiring pacemaker placement.
- Atrial flutter or fibrillation with rapid ventricular response requiring cardioversion.
- Ventricular fibrillation/flutter.
- At the discretion of the investigator, any arrhythmia classified as an adverse experience.

The enumerated list of major events of potential clinical concern are recommended as “alerts” or notifications from the core ECG laboratory to the investigator and Pfizer study team, and not to be considered as all-inclusive of what to be reported as AEs/SAEs.

## 10.8. Appendix 8: AEs, ADEs, SAEs, SADEs, USADEs, and Device Deficiencies: Definitions and Procedures for Recording, Evaluating, Follow-Up, and Reporting in Medical Device Studies

### Definitions of a Medical Device Deficiency

The definitions and procedures detailed in this appendix are in accordance with ISO 14155 and the European MDR 2017/745 for clinical device research (if applicable).

Both the investigator and the sponsor will comply with all local reporting requirements for medical devices.

The detection and documentation procedures described in this protocol apply to all sponsor medical devices provided for use in the study (see [Section 6.1.2](#) for the list of sponsor medical devices).

#### 10.8.1. Definition of AE and ADE

AE and ADE Definition

• An AE is defined in Appendix 2 (Section 10.2.1).

• An ADE is defined as an AE related to the use of an investigational medical device. This definition includes any AEs resulting from insufficient or inadequate instructions for use, deployment, implantation, installation, or operation, or any malfunction of the investigational medical device as well as any event resulting from use error or from intentional misuse of the investigational medical device.

#### 10.8.2. Definition of SAE, SADE, and USADE

SAE Definition

• An SAE is defined in Appendix 2 (Section 10.2.2).

SADE Definition

• An SADE is defined as an ADE that has resulted in any of the consequences characteristic of an SAE.

• Any device deficiency that might have led to an SAE if appropriate action had not been taken, intervention had not occurred, or circumstances had been less fortunate.

#### USADE Definition

- A USADE (also identified as UADE in US Regulations 21 CFR 813.3) is a SADE that by its nature, incidence, severity, or outcome has not been identified in the current version of the risk analysis management file.

#### 10.8.3. Definition of Device Deficiency

#### Device Deficiency Definition

- A device deficiency is an inadequacy of a medical device with respect to its identity, quality, durability, reliability, safety, or performance. Device deficiencies include malfunctions, use errors, and inadequate information supplied by the manufacturer.

#### 10.8.4. Recording/Reporting and Follow-Up of Medical Device Deficiencies

#### Device Deficiency Recording

- When a device deficiency occurs, it is the responsibility of the unblinded site staff to review all documentation (eg, hospital progress notes, laboratory reports, and diagnostic reports) related to the event.
- The unblinded site staff will then record all relevant device deficiency information in the participant's medical records, in accordance with the investigator's normal clinical practice, and will also capture the required information on the Medical Device Complaint form.
- It is **not** acceptable for the unblinded site staff to send photocopies of the participant's medical records to Pfizer Safety in lieu of following the reporting process described in the Medical Device Complaint form.
- There may be instances when copies of medical records for certain cases are requested by Pfizer Safety. In this case, all participant identifiers, with the exception of the participant number, will be redacted on the copies of the medical records before submission to Pfizer Safety.
- If the unblinded site staff determines that the medical device deficiency may have injured the participant (ie, the medical device deficiency is associated with an AE or SAE), then the unblinded site staff will attempt to establish a diagnosis of the event based on signs, symptoms, and/or other clinical information. Whenever possible, the diagnosis will be documented in the participant's medical record and recorded as the AE or SAE rather than the individual signs/symptoms. Requirements for recording and reporting an AE or SAE are provided in Appendix 2 ([Section 10.2.3](#)).

- For device deficiencies, it is very important that the unblinded site staff describes any corrective or remedial actions taken to prevent recurrence of the incident.
  - A remedial action is any action other than routine maintenance or servicing of a medical device where such action is necessary to prevent recurrence of a device deficiency. This includes any amendment to the device design to prevent recurrence.

#### **Assessment of Causality Occurring in Conjunction With a Medical Device Deficiency**

- If an AE or SAE has occurred in conjunction with a medical device deficiency, the investigator must assess the relationship between each occurrence of the AE or SAE and the medical device deficiency. The investigator will use clinical judgment to determine the relationship.
- A “reasonable possibility” of a relationship conveys that there are facts, evidence, and/or arguments to suggest a causal relationship, rather than a relationship cannot be ruled out.
- Alternative causes, such as underlying disease(s), concomitant therapy, and other risk factors, as well as the temporal relationship of the event to study intervention administration will be considered and investigated.
- The investigator will also consult the IB and/or product information, for marketed products in their assessment.
- For each device deficiency, the investigator **must** document in the medical notes that they have reviewed the device deficiency and have provided an assessment of causality.
- There may be situations in which an SAE has occurred and the investigator has **minimal** information to include in the initial report to the sponsor. However, it is very important that the investigator always make an assessment of causality for every event before the initial transmission of the SAE data to the sponsor.
- The investigator may change their opinion of causality in light of follow-up information and send an SAE follow-up report with the updated causality assessment.
- The causality assessment is one of the criteria used when determining regulatory reporting requirements.

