#### **6.1. Study Intervention(s) Administered**

Study interventions for this study will be:

Study Interventions		
Intervention Name	qIRV	QIV
Type	Vaccine	Vaccine
Targeted influenza strains	For each season - strains as recommended by WHO for influenza vaccines.	For each season - strains as recommended by WHO for influenza vaccines.

Study Interventions		
Intervention Name	qIRV	QIV
Unit dose strength(s)	Based on Phase 2 safety and immunogenicity data, the dose level of qIRV by age stratum is CC µg for participants 18 through 64 years of age and CC µg for participants $\geq$ 65 years of age.	As detailed in the IPM
Route of administration	Intramuscular injection	Intramuscular injection
Use	Experimental	Comparator
IMP or NIMP (global designation)	IMP	IMP
Sourcing	Provided centrally by the sponsor	Provided centrally by the sponsor or locally by the trial site (local sourcing by the trial site is not permitted without sponsor approval)
Packaging and labeling	Study intervention will be provided in a glass vial as open-label supply. Each vial will be labeled per country requirement.	Study intervention will be provided as either a PFS or a glass vial as open-label supply. Each dispensable unit will be labeled per country requirement.

If the primary efficacy analysis is not favorable, at the sponsor's discretion, the study may be unblinded early and, if still during the influenza season, participants who were randomized to receive qIRV may be offered a licensed QIV. This QIV will be considered NIMP, sourced locally by site and administered per the local package insert.

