### **6.1.2. Medical Devices**

The comparator vaccines detailed in [Section 6.1](#) may be provided as PFSs and, in which case, should be considered medical devices.

All medical device deficiencies (including malfunction, use error, and inadequate labeling) shall be documented and reported by the investigator throughout the clinical investigation (see [Section 8.4.9](#)) and appropriately managed by the sponsor.

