#### **6.4.2. Blinding of Site Personnel**

The study staff receiving, storing, dispensing, preparing, and administering the study interventions will be unblinded. All other study and site personnel, including the investigator and investigator staff, will be blinded to assignment of study intervention. In particular, the individuals who evaluate participant safety will be blinded. Because there are differences in physical appearance of qIRV and QIV, these study interventions will be administered in a manner that prevents the study participants from identifying the study intervention group based on its appearance.

The PI will assign the responsibility of the unblinded dispensers/administrators to persons who will not participate in the evaluation of any study participant. To ensure adequate coverage, at least 2 unblinded dispensers/administrators will be assigned per site. Members of the study site staff or clinic pharmacy should fulfill these roles. Contact between the unblinded dispensers and study participants should be kept to a minimum. The investigator, study coordinator, and any site staff other than the unblinded dispensers/administrators must not be allowed to know the study intervention assigned to any study participant and must not be allowed to see the study intervention container contents.

In the event of a Quality Assurance audit, the auditor(s) will be allowed access to unblinded study intervention records at the site(s) to verify that randomization/dispensing has been done accurately.

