#### **8.4.9. Medical Device Deficiencies**

Medical devices being provided for use in this study are those listed in [Section 6.1.2](#). In order to fulfill regulatory reporting obligations worldwide, the unblinded site staff is responsible for the detection and documentation of events meeting the definitions of device deficiency that occur during the study with such devices.

The definition of a medical device deficiency can be found in [Section 10.8](#).

Note: AEs and/or SAEs that are associated with a medical device deficiency will follow the same processes as other AEs or SAEs, as outlined in [Sections 8.4.1](#) through [8.4.4](#) and [Section 10.2](#) of the protocol.

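### Appendix 8 and Section 6.1.2 give the blinded investigator device-deficiency tasks that reveal QIV receipt when the deficiency is linked to a participant's dose; reconcile them with Sections 6.4.2 and 8.4.9

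*Protocol*

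**What the plan says.** **Supply.** In Protocol Section 6.1 the qIRV entry reads "Study intervention will be provided in a glass vial as open-label supply". The QIV entry reads "Study intervention will be provided as either a PFS or a glass vial as open-label supply". Section 6.1.2 says that the comparator vaccines "may be provided as PFSs and, in which case, should be considered medical devices". Section 8.4.9 and the opening of Appendix 8 both point to Section 6.1.2 for the list of study devices, and it names no other.

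**Blinding.** Section 6.4.2 blinds the investigator to every assignment. It also separates the roles from the other side: "The PI will assign the responsibility of the unblinded dispensers/administrators to persons who will not participate in the evaluation of any study participant".

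**Device tasks given to the investigator.** Section 6.1.2 says: "All medical device deficiencies (including malfunction, use error, and inadequate labeling) shall be documented and reported by the investigator", with a cross-reference to Section 8.4.9. In Section 10.8.4, for an AE or SAE occurring with a deficiency, "the investigator must assess the relationship between each occurrence of the AE or SAE and the medical device deficiency". The same section has the investigator note in the medical notes a review of each deficiency, and arrange evaluations into its nature and cause. Section 10.8.6 starts a 24-hour reporting clock when the investigator decides that an SAE-associated event is a deficiency.

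**Device tasks given to unblinded staff.** Section 8.4.9 says that "the unblinded site staff is responsible for the detection and documentation of events meeting the definitions of device deficiency". Sections 8.4.9.2 to 8.4.9.4 add follow-up, sponsor notification and reporting. The recording part of Section 10.8.4 has unblinded staff enter the deficiency in the participant's medical records. If the deficiency may have injured the participant, "then the unblinded site staff will attempt to establish a diagnosis of the event".

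**The concern.** In an observer-blinded trial of two products that look different, the blind rests on keeping those who handle the vaccine apart from those who assess the participant. The device text crosses that line in both directions. The investigator is given tasks that cannot be done without learning that a syringe was used. Unblinded staff are given a diagnostic task that Section 6.4.2 reserves for others, and they write arm-revealing information into a record that blinded staff use.

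Any leak is one-sided: it can expose QIV recipients but never qIRV recipients. The same investigator grades AE intensity and judges relatedness to study intervention (Section 10.2.3), so the exposed judgments are safety assessments in one arm. A site also cannot follow both sets of instructions where they assign the same task to different people.

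**Working it through.** No sample-size, power or error-rate figure is involved. The check is a cross-reading of the sections plus one logical step.

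**Step 1: what a deficiency reveals.** qIRV is supplied in vials only, and the only listed device is a QIV syringe. For a deficiency linked to a dose that a participant received, the probability that the dose was QIV is therefore 1. This does not extend to a syringe found defective and never linked to a participant. It does not arise at all where QIV is supplied only in vials.

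**Step 2: who does what.**

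| Task | Investigator (blinded) | Unblinded site staff |
|---|---|---|
| Detect and document | 6.1.2 (document), cross-referring to 8.4.9 | 8.4.9; 10.8.4, recording |
| Report to sponsor | 6.1.2, same cross-reference | 8.4.9.3, 8.4.9.4 |
| Decide that the event is a deficiency | 10.8.6, if SAE-associated | 8.4.9.3, by implication |
| Follow up nature and cause | 10.8.4, follow-up | 8.4.9.2 |
| Review each deficiency | 10.8.4, causality | not assigned |
| Judge AE/SAE against the deficiency | 10.8.4, causality | not assigned |
| Diagnose the associated AE/SAE | role implied by 6.4.2 and 10.2.3 | 10.8.4, recording |

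**Step 3: sort the conflicts.**
- *Follow-up* is a direct contradiction. Sections 8.4.9.2 and 10.8.4 give essentially the same duty to different people.
- *Determination* also conflicts. Section 8.4.9.3 counts 1 business day from a determination that it implies unblinded staff make. Section 10.8.6 counts 24 hours from the investigator's determination.
- *Review and AE-to-device causality* do not conflict with Section 8.4.9, which assigns neither. They conflict with Section 6.4.2, because neither can be done for a dosed participant without disclosing QIV.
- *Diagnosis by unblinded staff* conflicts with the role separation in Section 6.4.2.
- *Documenting and reporting in Section 6.1.2* is the weakest conflict, because that sentence sends the reader to Section 8.4.9.

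**Step 4: look for a masked route.** The device sections describe none. Emergency unblinding in Section 6.4.4 is a separate case-by-case safety decision and does not cover routine deficiency review.

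**The case against.** The strongest reply is that Section 8.4.9 is the operative procedure and already protects the blind: Section 6.1.2 points to it and the recording part of Section 10.8.4 agrees with it. On that view the remaining mentions of the investigator are leftover wording. This is fair for routine documentation and reporting, and a reader should not infer that the plan simply makes the blinded investigator the reporter of every deficiency. It does not answer the review, causality and follow-up duties in Section 10.8.4 or the determination in Section 10.8.6, which carry no such cross-reference.

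Two stronger readings are tempting, and the documents do not support them.

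- *Bias in the primary endpoint.* A reader might reason that an unblinded investigator controls which illnesses are swabbed. Under Section 8.10.6, however, ILI contact is started by the participant from listed symptoms, whatever their suspected cause, with weekly prompts. Beyond confirming those symptoms, the investigator's discretion concerns the 7 days after vaccination, which fall before the Day 15 start of the endpoint window (SAP Section 3.1.1.2), and whether later symptoms are a second ILI. Swabs may be self-collected, cases need central laboratory confirmation, and samples are coded (Protocol Sections 8.2.1 and 8.2.3). The route to a biased RVE is thin.
- *A count of unblinded participants.* Halving the 53,200 ceiling gives 26,600, and an assumed deficiency rate of 0.1% to 1% gives about 27 to 266. The documents give no such rate, and the randomization ratio is redacted. The total is an upper limit and QIV may come in vials. The sum also needs every deficiency to be linked to a dose and to reach the investigator. The range should not be used.

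**Conclusion.** The point holds as an internal inconsistency with a blinding consequence. When a device deficiency is linked to a participant's dose, following Sections 10.8.4 and 10.8.6 as written tells the investigator that the participant received QIV, which Section 6.4.2 forbids. Section 10.8.4 also gives unblinded staff a diagnostic role that Section 6.4.2 excludes, and it contradicts Section 8.4.9.2 outright on follow-up.

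The size cannot be estimated from the documents. That it is probably small is a judgment, since the documents give no rate. It would be zero where QIV is supplied only in vials. What is exposed is mainly blinded AE grading and causality assessment in the affected QIV recipients, with little expected effect on the primary RVE. The conclusion rests on the supply table in Section 6.1 and the device list in Section 6.1.2 being complete.

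**What to change.** Reconcile Sections 6.1.2, 10.8.4 and 10.8.6 with Sections 6.4.2 and 8.4.9:

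1. Name unblinded site staff for detecting, documenting, reporting, determining and following up device deficiencies.
2. Keep the deficiency record on the Medical Device Complaint form in the unblinded file, and remove the instruction to enter it in the participant's medical record.
3. Leave AE/SAE diagnosis, and causality in relation to study intervention, with the blinded investigator.
4. Assign the AE-to-device causality judgment to a designated unblinded, medically qualified person who does not evaluate participants. If the sponsor's unblinded clinicians in Section 6.4.3 are chosen, amend that section too, because it now bars them from other study activities.
5. Leave emergency unblinding in Section 6.4.4 as it is, and add no rule that withholds safety information from the investigator. The change concerns who handles and judges the device deficiency, not what may be communicated for a participant's safety.

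The cost is rewording in a few sections and a small added task for an unblinded role.
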